#### 4.6 Follow-up study visits and retention efforts

After enrollment and randomization assignment (including amlodipine initiation), participants will have follow-up visits either at GHESKIO (months 0.5-1, 3, 6, 9, 12) or in the community / home with CHWs (months 2, 5, 8) (table 4). All visits will include BP measurement, lifestyle counseling, adherence encouragement, and assessment of adverse events. The GHESKIO visits will also include a physical exam. Participants in the early intervention arm will receive monthly amlodipine refills. Participants in the SOC arm will initiate amlodipine only if they develop hypertension (SBP  $\geq 140$  or DBP  $\geq 90$  mm Hg).

At the 12-month study visit, participants will also complete a brief questionnaire about changes in health behaviors and have viral load measured. Participants may return to the HIV clinic at any time for symptoms, questions, or other concerns, and a BP measurement will be taken at each of these encounters. Adverse events will be assessed at each visit. Medical record abstraction will be done by research staff for any hospitalization or death among a participant.

To encourage retention and minimize missing data, GHESKIO staff will call participants 1-2 days prior to each study visit and will also call and track participants who miss a scheduled study visit. Since 2012, GHESKIO has recruited HIV-infected adults for 16 HIV trials with 98% retention.

#### 4.7 Study Measures and Schedule

Description of study measures and their schedules are listed in table 4.

**Table 4: Study Measures and Schedule**

Required forms:	SCREEN	ENROLL	M1	M2	M3	M5	M6	M8	M9	M12
Screening Eligibility Form: inclusion criteria, exclusion criteria	X									
Screening Labs: urine/serum pregnancy test, fasting or random glucose, Creatinine	X									
Individual Characteristics										
Locator information: address and cell phone, friend/family member's cell phone		X	X	X	X	X	X	X	X	X
Sociodemographics: age, sex		X								
Socioeconomic factors: income, education, occupation, marital status, children.		X								
Medical History: history of CVD risk factors, CVD, HIV, tuberculosis		X								
Family History: stroke or MI in parents and 4 oldest siblings		X								
Health behaviors: current cigarette smoking,  alcohol  , physical activity 		X								X
Multidimensional Poverty: child death, educational attainment, household construction materials, possessions		X								
Clinical Measures										
Physiologic: height, weight		X								

Blood pressure in community		X		X		X		X		
Blood pressure at clinic		X	X		X		X		X	X
ECG		X								
Echocardiography and vascular ultrasound		X								
Enrollment Labs: HgbA1c, total cholesterol, HDL, CD4, VL		X								
12M Labs: VL										X
Medical record abstraction: diagnoses codes (ICD-9), laboratory measures, diagnostic imaging, and cause of death among participants who receive clinical care from the GHESKIO NCD clinic, a GHESKIO-affiliated hospital, or other health facility			X	X	X	X	X	X	X	X
Clinical Management										
Medication Adherence		X	X	X	X	X	X	X	X	X
Medical record abstraction for development of HTN after enrollment			X	X	X	X	X	X	X	X
Medical record abstraction for clinical management of CVD risk factors: smoking, HLD, DM		X	X	X	X	X	X	X	X	X
Intervention related										
Amlodipine initiation form		X								
In depth interviews about feasibility, acceptability				X	X	X	X	X	X	X
Adverse Events				X	X	X	X	X	X	X

**BP measurement:** All BP measurements will follow AHA/WHO guidelines using semi-automated electronic cuffs (OMRON 742-5 series at home and HEM907 in clinic) of 3 BPs separated by  $\geq 1$  minute with the individual seated at rest. The average of the 3 BPs is the BP for the visit.

**HIV services for all participants:** Provision of HIV services, including ART, adhere to national guidelines. The first-line ART regimen is TDF/3TC/dolutegravir; second-line regimens include protease inhibitors. Patients who are virally suppressed are seen in the GHESKIO HIV clinic every 6 months for adherence assessment and medication refills. HIV-1 RNA viral load is measured annually. BP is measured at every clinic visit.

**Early HTN treatment vs. SOC procedures:** The only difference between study arms is the BP threshold at which amlodipine is initiated. Participants in the early HTN treatment arm will initiate amlodipine 5 mg immediately followed by an increase to 10 mg if SBP  $>130$  mm Hg after 1 month or more. Participants in the SOC arm will initiate the same algorithm but at the standard BP threshold for HTN which is SBP  $\geq 140$  or DBP  $\geq 90$  mm Hg in two measurements on different days. There are no known drug-drug interactions between the first-line ART and amlodipine. Haiti's guidelines recommend amlodipine as the first line regimen for diabetic individuals as well.

**Clinical management of CVD risk factors and diseases:** Any participant diagnosed with a risk factor or disease through study procedures will be escorted to the GHESKIO clinic or affiliated hospital in Port-au-Prince for clinical care and further evaluation by clinicians who are independent of the research team (see Human Subjects). Clinical care is provided free of charge.

**Study Outcomes:** The primary quantitative outcome is the difference in mean change in SBP (mm Hg) between study arms at 12 months. Secondary outcomes include **viral suppression** defined per WHO guidelines of HIV-1 RNA <1,000 copies/ml and amlodipine and ART **medication adherence** defined as >90% adherence using 3-day pill recalls, as recommended by the ACTG at enrollment, 3, 6, 9 and 12 months. We will assess for serious **adverse events** including DAIDS Grade III-V symptoms of hypotension, peripheral edema and other symptoms related to medications at every study visit (see Human Subjects). **Feasibility and acceptability** will be assessed by enrollment and retention statistics as well as qualitative in-depth interviews among a subset of 30 participants in the early HTN treatment arm and all study providers at 12 months. We will assess participant attitudes towards the study drug amlodipine. Interviews will explore attitudes about initiating amlodipine, positive/negative effects, satisfaction, intent to continue, home BP measurement, and perceived CVD risk. We will interview providers about implementation challenges and unintended consequences. Interviews will be ~45 minutes, conducted in Creole, audio-recorded, transcribed verbatim, and translated into English for analysis using Atlas-ti. Among all participants, we will measure **CVD risk factors** at enrollment (Table 5). In participants  $\geq 40$  years, we will calculate their 10-year AHA atherosclerotic CVD (ASCVD) risk at enrollment. Pre-existing **myocardial and vascular dysfunction** will be measured at enrollment using ECG, echocardiogram, and vascular ultrasound (Sonosite M-Turbo ultra-sound with P21-x probe). Dysfunction is defined as evidence of left ventricular hypertrophy, diastolic and/or systolic dysfunction, ischemia, increased carotid intima media thickness (surrogate for atherosclerosis), and carotid-femoral pulse wave velocity (measure of arterial stiffness) using imaging criteria from the American and European Societies of Echocardiography and Minnesota criteria. [name] is trained and certified in echocardiography and has experience measuring these parameters with quality assurance from Cornell cardiology in the NHLBI R01 HL143788.

**Table 5: CVD risk factors**

**Factors included in ASCVD:** gender, age, race (white or other), total cholesterol (mg/dL), HDL cholesterol (mg/dL), SBP, received treatment for HTN, diabetes (HbA1c  $>7$  or on medications), smoking

**Other CVD factors:** BMI (kg/m^2), waist circumference, poor diet (WHO STEPS), physical inactivity (WHO STEPS), CD4 count, viral load

#### 4.8 Research staff training and data management

Research staff will be trained in Good Clinical Practice and will receive training for study procedures and a training on AHA/WHO BP measurement guidelines including certification prior to study enrollment and recertification every 6 months. Participants will be identified by an unique study ID number and no participant identifying information will be recorded. Data on research forms will be entered by a data clerk and supervised by [name] (Data Manager) into NIH-approved REDCap data management system, which is encrypted, and password protected. [name] and [name] will oversee data quality control and assurance using CTU procedures. They will review consent documents and REDCap data files for internal validity and completeness. [name] will travel monthly to Haiti to meet with the study team and will participate in weekly conference calls with [name].

#### 4.9 Analysis plan and statistical power considerations

**Sample size and power:** With a sample of 250 participants and 6 time points for BP measurements for each participant, we have 80% power with alpha 0.05 to detect a difference in change in SBP of 4 mm Hg or more between the study arms at 12 months (assuming consistent difference across time and a conservative correlation among measurement of 0.95). We will present summary statistics (e.g., mean and SD of pre, post, and difference within and between arms) in publication for readers and future meta-analyses.

**Aim 1:** Feasibility will be measured as the proportion of eligible participants willing to participate in the trial and their retention, and the proportion initiating amlodipine. We will compare the mean difference in change in SBP among participants from enrollment to 12 months in each study arm using linear mixed-effects model (LMM) accounting for repeated measures and correlations within subjects, where the time\*treatment interaction will serve as “primary” parameter addressing differential slopes for the two arms. We anticipate the two arms will have similar baseline characteristics due to randomization, and therefore the primary analysis will not adjust for baseline variables. If baseline variables are imbalanced, we will adjust factors in regression and report as sensitivity analysis. We will assess incidence of HTN using Kaplan Meier methods. We will analyze dichotomized outcomes (SBP <120 and DBP <80) at all time points via generalized mixed-effects model and at 12 months via Fisher exact tests and logistic regression. In other sensitivity analyses, we will explore the following issues: 1) compliance/adherence (e.g., per protocol analysis); 2) missing data/dropout (via last-value-carried-forward, multiple imputation or inverse-probability weighting); 3) competing risks (e.g., death); 4) joint modeling (of longitudinal and survival data); and 5) changepoint (of treatment initiation in SOC arm).

**Aim 2:** The proportion of participants in each study arm with viral suppression (HIV-1 RNA < 1000 copies/mL) at 12 months will be compared between study arms using the Fisher exact test; we assume participants who are lost to follow-up or dead at 12 months will have HIV-1 RNA > 1000 copies/mL. Other categorical data including medication adherence, CVD risk factors (e.g. diabetes) will be analyzed similarly. Longitudinal data such as BMI and adherence (continuous or binary/categorical) will be analyzed accounting for repeated measures within participants, via LMM and GLMM as described above. We will also consider Generalized estimating equation-based method (so called, marginal or population-averaged model) and will report consistency or meaningful discrepancy. Acceptability will be assessed in qualitative interviews by [name] who is trained in qualitative research using interview information transcribed verbatim, translated into English, and then coded for analysis using a thematic coding scheme. We will also describe adverse events among all participants.

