## Protocol Summary

**Title:** Prehypertension in Haiti

**Study Summary:** We propose an unblinded pilot RCT of 250 persons living with HIV (PLWH), aged 18-65 years, who receive ART care at GHESKIO, are virally suppressed, and have pre-HTN (SBP 120-139 or DBP 80-89 mm Hg) to be randomized to **early HTN treatment** versus **standard of care** (SOC). Participants will be recruited from GHESKIO's HIV clinic. Eligible individuals will complete informed consent and be randomized to early HTN treatment vs. SOC. Participants in early HTN treatment will initiate amlodipine immediately versus those in SOC will initiate amlodipine only if they meet the HTN threshold during the study period. All participants will be followed for 12 months. The primary outcome is mean change in SBP at 12 months between study arms. Secondary outcomes are viral suppression, medication adherence, adverse events, and acceptability. We will also assess CVD risk factors and myocardial/vascular dysfunction among all participants at enrollment.

**Population:** We will recruit 250 PLWH from GHESKIO'S HIV Clinic. Inclusion criteria: PLWH 18-65 years of age, ART duration  $\geq$  1 year , stable regimen  $\geq$  6 months, HIV 1-RNA  $<$  1,000 copies/mL within past 12 months, Pre-HTN (SBP 120-139 or DBP 80-89 mm Hg), no current antihypertensive treatment, receives HIV care at GHESKIO, and willing to provide consent. Exclusion criteria: pregnancy, kidney disease, diabetes, advanced illness with limited life expectancy, plans to move out of the area within the next year, and clinician determination that patient is unstable on ART.

**Number of Sites:** Single site: GHESKIO Center Port au Prince, Haiti

**Study Duration:** 2 years

**Subject Duration:** 12 months

**Primary Aim:** To assess the feasibility of initiating antihypertensive treatment among PLWH with pre-HTN through a pilot randomized controlled trial comparing early HTN treatment to SOC. Feasibility outcomes include enrollment and retention data, proportion who initiate amlodipine, and incremental change in SBP at 12 months between arms. The pilot trial has  $\geq$ 80% power to detect differences in change in SBP  $\geq$  4 mm Hg.

**Secondary Aims:** To also examine the following outcomes and measures:

- a. Viral suppression compared between study arms at 12 months (defined as HIV-1 RNA  $<$  1000 copies/ml)

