- b. HIV medication adherence compared between study arms at 6 and 12 months (defined as  $>$ 90% adherence using 3-day pill recalls)
- c. Adverse events compared between study arms at 12 months (defined as Grade III-V adverse events including hypotension, peripheral edema, and other symptoms which may be related to amlodipine)
- d. Acceptability assessed through in-depth interviews with a subset of participants and providers

- e. CVD risk profile measured among all participants at enrollment including obesity, dyslipidemia, diabetes, smoking, physical inactivity, poor diet, and 10-year CVD risk (only among participants  $\geq$  40 years)
- f. Pre-existing myocardial and vascular dysfunction measured among all participants at enrollment using ECG, echocardiography and vascular ultrasound

**Study endpoints and analysis:** The primary endpoint is the difference in mean change in SBP (mm Hg) between study arms at 12 months. Secondary outcomes include viral suppression and medication adherence. We will also measure CVD risk factors among participants. We will compare the mean difference in change in SBP among participants using a linear mixed-effects model (LMM) accounting for repeated measures and correlations within subjects. We will assess incidence of HTN using Kaplan Meier methods. Dichotomized outcomes such as HTN will be analyzed via generalized linear mixed-effects model (GLMM) at all time points and via Fisher's exact test and logistic regression at 12 months. Viral suppression, medication adherence, and CVD risk factors will be compared between study arms using Fisher's exact test. Longitudinal data such as BMI and adherence will be analyzed using LMM and GLMM.

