**Figure 2: Survival of HIV-infected adults with and without HTN at ART initiation**

We analyzed a more recent cohort of 762 PLWH who initiated ART between 2013-2015 at GHESKIO and found HTN prevalence at time of ART initiation doubled to 12% and HTN incidence tripled to 108/1000 person-years (Table 1). Of note, 38% of PLWH with pre-HTN at time of ART start developed incident HTN within 18 months. We postulate that the GHESKIO ART Cohort had a higher number of persons with AIDS at ART start as compared to this later cohort.

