- E. Adverse events: Amlodipine is recommended by the WHO as first-line medication for elevated blood pressure and has a safe side effect profile. The most common side effects of amlodipine are dizziness and or lightheadedness and peripheral edema. We will monitor adverse events using DAIDS criteria for hypotension, peripheral edema and other side effects reported by participants that are related to amlodipine. In other studies, a dose of amlodipine 10mg daily is associated with ~ 5-6 mm Hg reduction in SBP over 1 month. In one clinical trial (CAMELOT), which evaluates the use of amlodipine 10 mg daily among normotensive adults with existing cardiovascular disease, 3.3% of participants reported symptoms of lightheadedness and dizziness for which amlodipine was discontinued and 5% discontinued amlodipine due to peripheral edema. We anticipate a similar rate of side effects and adverse events in this study.

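### The primary model parameter in Section 4.9 is a difference in slopes, which is not the month-12 difference in SBP change that the plan defines as its primary endpoint

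*Combined protocol and SAP*

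**What the plan says.** The endpoint is stated consistently. Protocol Summary: "The primary endpoint is the difference in mean change in SBP (mm Hg) between study arms at 12 months". Section 4.7, Study Outcomes: "The primary quantitative outcome is the difference in mean change in SBP (mm Hg) between study arms at 12 months". Section 4.9, Aim 1, opens with the same comparison, from enrollment to 12 months, in a linear mixed model. It then names the time-by-treatment interaction as the primary "parameter addressing differential slopes for the two arms". It does not say whether time enters as a continuous variable or as visit categories.

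The power paragraph of Section 4.9 uses 250 participants and six time points to claim 80% power for 4 mm Hg at 12 months, "assuming consistent difference across time and a conservative correlation among measurement of 0.95". No SD and no sidedness are given. The Protocol Summary repeats the claim of at least "80% power to detect differences in change in SBP" of 4 mm Hg or more.

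Three other statements bear on the shape of the effect over time:
- Section 3.1: "a dose of amlodipine 10mg daily is associated with ~ 5-6 mm Hg reduction in SBP over 1 month".
- Section 4.6: "Participants in the SOC arm will initiate amlodipine only if they develop hypertension".
- Section 2.1, from a cohort at ART start: "38% of PLWH with pre-HTN at time of ART start developed incident HTN within 18 months".

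**The concern.** A slope is a rate estimated from all visits; the endpoint is a difference at one visit. Twelve times the monthly slope difference equals the month-12 difference in change only if the gap between arms grows in a straight line from enrollment.

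The plan's own material does not suggest a straight line. The drug effect it cites appears within a month, although at the 10 mg dose. Control participants who become hypertensive start the same drug, which would narrow a later gap. The power paragraph itself assumes a constant difference, and a difference that is constant over the post-enrollment visits has zero slope across them.

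If the effect comes early and then holds, the parameter labelled primary can understate the stated endpoint. That matters because the estimate is meant to inform the design of a larger trial, and a reader will compare the primary result with the 4 mm Hg in the power statement. The power statement cannot guide that reading either, because it is unclear which quantity it is for.

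**Working it through.** **Inputs.** From the plan: 250 participants randomized 1:1, so n = 125 per arm; six time points, taken as enrollment and clinic months 1, 3, 6, 9 and 12 (Sections 4.6 and 4.9); alpha 0.05; difference 4 mm Hg; correlation 0.95. Assumed: two-sided test, normal approximation, complete data, and every effect shape, covariance and SD below.

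**Step 1: the plan's 80%.** It cannot be reproduced without an SD, so I solve for the SD that yields 80%, using 1.960 + 0.842 = 2.802 and compound symmetry with correlation 0.95.
- Time-averaged difference: SE = SD x sqrt[(2/125)(1 + 5 x 0.95)/6]. Setting 4/SE = 2.802 gives SD = 11.5.
- Month-12 change: SE = SD x sqrt[4(1 - 0.95)/125]. SD = 35.7.
- Slope x 12: SE = 12 x SD x sqrt[2(1 - 0.95)/(125 x Sxx)], with Sxx = 271 - 31²/6 = 110.83. SD = 44.3.

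With SBP at entry largely 120 to 139, only the first SD is believable. At SD 11.53 (the unrounded value), time-averaged power falls as correlation rises: 95%, 92%, 85% and 80% at 0.5, 0.6, 0.8 and 0.95. Month-12 change power rises: 78%, 87%, 99% and over 99%.

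**Step 2: slope against endpoint.** Each shape has a true month-12 difference of 4. Under compound symmetry the slope is the least-squares slope of the between-arm profile on time (mean time 31/6 = 5.17). A random intercept-and-slope covariance gives the same values with complete data.

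| Shape (months 0, 1, 3, 6, 9, 12) | Slope x 12, compound symmetry | Slope x 12, AR(1), monthly 0.9 to 0.95 |
|---|---|---|
| Full by month 1: 0, 4, 4, 4, 4, 4 | 12 x 20.67/110.83 = 2.24 | 3.77 to 3.93 |
| Half at month 1: 0, 2, 4, 4, 4, 4 | 12 x 29.00/110.83 = 3.14 | 3.86 to 3.96 |
| Ramp: 0, 1.5, 3, 4, 4, 4 | 12 x 33.25/110.83 = 3.60 | 3.92 to 3.98 |
| Narrowing: 0, 2.61, 5.08, 4.69, 4.33, 4.00 | 12 x 25.98/110.83 = 2.81 | 3.81 to 3.94 |
| Linear | 4.00 | 4.00 |

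The narrowing shape has half the effect at month 1 and all of it by month 3, less the control share on treatment. That share is 1 - 0.62^(t/18), a constant rate fitted to the 38% in 18 months, and reaches 27% at month 12. The curve is scaled to 4 at month 12. It assumes that control participants who start get the full effect.

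Reading the fitted month-12 gap off the same linear model does not help: for the first shape it is 2.37 + 2.24 = 4.61.

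**Step 3: power of the two tests.** Illustration at SD 11.53, correlation 0.5, compound symmetry. SE of slope x 12 = 1.175; SE of month-12 change = sqrt(4 x 11.53² x 0.5/125) = 1.458. The month-12 contrast has 78.3% power for every shape. The slope test has 48% (full), 76% (half), 86.5% (ramp), 67% (narrowing) and 92.5% (linear). At correlation 0.95 all are near 100%.

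**Step 4: correlation and the month-12 contrast.** Detectable difference = 2.802 x SD x sqrt[4(1 - correlation)/125].

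| SD | Correlation 0.5 | Correlation 0.95 |
|---|---|---|
| 10 | 3.54 | 1.12 |
| 12 | 4.25 | 1.34 |
| 15 | 5.32 | 1.68 |

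**The case against.** The best defence is that the interaction was meant with visit as a category. Its month-12 term would then be the endpoint and the mismatch would vanish. Aim 1 does open with change from enrollment to 12 months. But the text speaks of slopes and never defines time, and a categorical interaction over six visits has five terms, of which none is named as primary. So the defence shows that the cure is easy, not that the plan already has it.

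The size is also open to challenge, and much of that stands. The 2.24 is an extreme case, since treatment starts at 5 mg and the cited one-month fall is at 10 mg. Under AR(1) the gap is at most 4.00 - 3.77 = 0.23 mm Hg. At the plan's only stated correlation no power loss appears. The 27% control uptake comes from people starting ART, whereas trial entrants have had at least a year of it and are suppressed.

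Section 4.9 also lists a changepoint analysis for treatment start in the control arm, and promises raw pre, post and difference summaries by arm. Both soften the consequence; neither changes which parameter is primary.

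Two stronger readings are tempting. One is that the plan mislabels a favourable correlation as conservative. The documents do not support this: the constant difference, the six time points and the back-solved SD all point to a time-averaged difference, for which the label is right. The formula is not printed, so that too is inference. The other is that the slope would govern what Section 3.2 says about treatment after the trial. That section refers to the primary study outcome, which Section 4.7 defines as the month-12 difference.

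**Conclusion.** Wrong as written: the parameter named as primary does not match the stated endpoint. For a true month-12 difference of 4 mm Hg, the slope-based figure falls short by 0 to 1.76 mm Hg under compound symmetry (4.00 - 2.24) and by 0 to 0.23 under AR(1), depending on shapes and covariances that the plan does not fix. Separately, the 80% power can be neither confirmed nor refuted, because no SD is given; it appears to belong to a quantity that is neither the endpoint nor the slope. Confidence is moderate: the slope mismatch depends on reading time as linear, and the power reading is inferred. The trial is a feasibility pilot, which limits the consequence, but the correction is cheap and should be made before analysis.

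**What to change.** In Section 4.9, state that the mixed model treats visit as categorical with enrollment SBP as the first visit. Name the arm contrast in SBP change from enrollment to month 12 as the single primary parameter. Keep the linear time-by-treatment slope as secondary. The covariance structure can be left to the trial statistician, provided it is fixed before analysis.

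Restate the power in Section 4.9 and in the Protocol Summary for that contrast, giving the assumed SD, sidedness and a range of correlations. Do not carry the conservative label for 0.95 over to it.

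The cost is wording, plus eight more fixed-effect terms with six visits (12 visit-by-arm means against 4 coefficients). No new data or participants are needed. The drawback is some power if the effect builds gradually: at SD 11.53 and correlation 0.5, 78.3% against 86.5% for the ramp and 92.5% for a linear effect. Power is about equal with half the effect at month 1 (78.3% against 76%), and better if the full effect comes by month 1 (against 48%) or the gap narrows later (against 67%).
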